## Table 8.1-3 Schedule of events, Part B (MAD) Part B (MAD)

BMI=Body mass index. CTP=Clinical trial protocol. ECG=Electrocardiogram. FSH=Follicle stimulating hormone.

1. Details in separate flow charts (Table 8.1-4 and Table 8.1-5).

2. The duration of the intervention and observation period in Part B may be adjusted (8 days BID dosing duration

assumed). 3. Or after early withdrawal.

- 4. Females only (questionable cases).
- 5. Drug tests may also be performed at 1 to 2 additional random occasions during the trial.
- 6. Symptom driven physical examination
- 7. Clinical chemistry, haematology and coagulation, see Section 11.3.5.
- Systolic and diastolic blood pressure, pulse, respiratory rate at all visits indicated. Temperature will be measured on Day -1 only (other visits if indicated). For details regarding vital signs, see Section 11.3.4.
- 9. Metabolite profiling in plasma and urine at steady state only (Day 8 to Day 10).
- 10. Cohort B4 only. The EndoPAT assessment will be performed before the first IMP administration (Day -1 or Day 1) and 30±10 minutes after IMP administration on Day 7 (morning or evening dose). Subjects must fast for at least 4 hours prior to the EndoPAT assessment until end of assessment.
- 11. Breakfast at least 1-hour post-dose. Day -1 to Day 1 and Day 7 to Day 8: Standardised breakfast, lunch, snack, dinner and optional evening snack as applicable. Non-standardised meals Day 2, 3, 4, 5, 6, 9 and 10. For timing of meals, refer to Table 8.1-4 and Table 8.1-5.

# Table 8.1-4 Detailed schedule of events, Part B (MAD) Day -1 to Day 7

Day	Day -1							Day 1							Da	y 2	Da	Day 3 Days 4 to 7		
Assessment/time- point (hh:mm)	Ad- mission	Pre- dose	00:00	00:20	00:40	01:00	01:30	02:00	03:00	04:00	06:00	08:00	10:00	12:00	24 h	36 h	48 h	60 h	D4: 72 h D5: 96h D6:120 h D7:144h	D4:84h D5: 108h D6:132 h D7: 156 h
Inclusion/ exclusion criteria	Х	х																		
Urine drug screen	X																			
Alcohol test	Х																			
Physical examination		X1																		
Clinical laboratory. Profile	Х																X 		X 	
Safety urine sampling	Х																X 		X 	
Urinalysis (dipstick)	Х																			
Vital signs 	x	X			Х			Х		X	X		Х		X5		X5		X5	
12-lead ECG		X			X			X		X	X		X		X5		X5		X 	
Randomisation		X																		
IMP administration			X											Х	X	X	X	Х	Х	Х
Blood sampling for PK		x		x	x	X	x	x	X	x	X	x	x	X 	X6		X6		X 	
Urine sampling for PK 		X						2	K 											
PD (EndoPAT) assessment 		х																	Х	
Meals 										Х										

CONFIDENTIAL

Adverse events	X				
Prior and concomitant meds.	X				
1 Symptom driven physical examination					

- 1. Symptom driven physical examination.
- 2. Clinical laboratory profile Day 3: pre-dose and Day 6: pre-dose.
- 3. Safety urine sampling Day 3 pre-dose and Day 6 pre-dose.
- 4. Systolic and diastolic blood pressure, pulse, respiratory rate at all time points indicated. Temperature will be measured on Day -1 only (other visits if indicated). For details regarding vital signs, see Section 11.3.4.
- 5. Vital signs and ECG Day 2 to Day 7: both in association with the morning dose and the evening dose, pre-dose and 1-hour post-dose.
- 6. Day 1: pre-dose at 12 hours. Day 2: pre-dose at 24 hours. Day 3 to Day 7: trough concentration (Ctrough) pre-morning dose samples, see Section 11.4.1.
- 7. PK urine sampling pre-dose and 0-12 hours post-dose.
- 8. Cohort B4 only. The EndoPAT assessment will be performed before the first IMP administration (Day -1 or Day 1) and 30±10 minutes after IMP administration on Day 7 (morning or evening dose). Subjects must fast for at least 4 hours prior to the EndoPAT assessment until end of assessment.
- 9. Standardised meals on Day -1, Day 1, Day 7 and Day 8, non-standardised meals on Day 2 to Day 6. Breakfast at least 1 hour post dose, lunch, snack, dinner and optional evening snack at approximately 4, 7 and 9 and 10 h post-dose. Optional evening snack at least 2 hours before or 1 hour after IMP administration.

#### Table 8.1-5 Detailed schedule of events Part B (MAD) Day 8 to Day 10

Day		-			-	-	D	ay 8							Day 9	Day 10
Assessment/time-point (hh:mm)	Pre- dose	00:00	00:20	00:40	01:00	01:30	02:00	03:00	04:00	06:00	08:00	10:00	12:00	16:00	24 h post last dose	48 h post last dose
Clinical Laboratory profile	X															X
Safety urine sampling	X															X
Urinalysis (dipstick)	X															
Vital signs	X			X			X		Х	X		X			X	X
12-lead ECG	X			X			X		Х	X		X			X	X
IMP administration		Х														
Blood sampling for PK and metabolite profiling	X1		X	X	X	X	X	X	X	X	Х	X		X	Х	X
Urine sampling for PK and metabolite profiling 			X 													
Meals 		X														
Adverse events		X														
Prior and concomitant medications.								-	X							

1. Trough (pre-dose) sample on Day 8, see Section 11.4.1.

2. PK urine sampling 0-12 hours post last dose (*i.e.*, morning dose Day 8).

Day 8: Standardised breakfast at least 1 hour post dose on Day 8, standardised lunch, snack, dinner and optional evening snack at approximately 4, 7 and 9- and 11-hours post-dose. Day 9: Non-standardised breakfast after PK sampling. Lunch, snack, dinner and optional evening snack at approximately 4, 7 and 9 and 11 h post-dose. Day 10: Breakfast only.

# 8.2 Rationale for trial design

The EMA guideline on strategies to identify and mitigate risks for FIH and early clinical trials with IMPs (EMEA/CHMP/SWP/28367/07 Rev. 1) has been considered.

The design of the trial is based on the aim to study safety, tolerability, and PK (including influence of food) of selected doses of C106 in a limited number of healthy volunteers. The design is adaptive, to allow for *e.g.*, flexible dose escalation and involves careful monitoring of the subjects' well-being. The time points for PK blood sampling are selected based on data obtained from previous non-clinical studies.

A placebo control will be used to establish the frequency and magnitude of changes in endpoints that may occur in the absence of active treatment.

Randomisation will be used to minimise bias in the assignment of subjects to dose groups and to increase the likelihood that known and unknown subject attributes (e.g., demographic and baseline characteristics) are evenly balanced across treatment groups.

Blinded treatment will be used to reduce potential bias during data collection and evaluation of endpoints.

For both Part A (SAD) and Part B (MAD) of the trial, a sequential-cohort, sentinel-dosing, ascending-dose design has been chosen for safety reasons as C106 is in early stage of clinical development, with Part A of the trial being the first time C106 will be administered to humans. Conducting the initial SAD and MAD trial with C106 in healthy subjects mitigates the potential confounding effects of the disease state and concomitant medications.

Oral administration has been chosen for all parts of the trial, as this is the intended clinical route of administration.

A 2-part cross-over design has been chosen for the food-effect evaluation, as a within-subject assessment of the influence of food on the PK of C106 increases the power for the given number of subjects.

An exploratory PD assessment will be performed in Part B (MAD), cohort B4 to investigate the effect of C106 on endothelial function. This data may support future trials on IPF-associated vasculopathy and further use of this PD assessment in early clinical development programs.

Overall, the trial will provide important data to support the design of further studies, both in healthy volunteers and in patients.

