# 6.1.4 Non-clinical pharmacokinetics and drug metabolism

Pharmacokinetic studies of C106 have been performed in rats following oral and intravenous administrations and in dogs after oral administration. The oral route is the intended route of administration in the clinical development program. *In vitro* studies have been conducted to evaluate plasma protein binding, metabolic stability, metabolite identification, and involvement of enzymes to investigate the potential of metabolic interactions.

Following intravenous administration in rats, C106 is classified as an intermediate clearance compound with an intermediate terminal half-life of about 2 h.

C106 was absorbed rapidly after single and repeated oral administration with maximum plasma concentration  $C_{max}$  reached within 1-4 h in rats and dogs, followed by a prolonged elimination from the plasma and an elimination half-life (t1/2) of 2.9 to 11 h in rats and 1 to 4.6 h in dogs. No accumulation of C106 was observed following repeated once daily oral administration for up to 28 days in rats and dogs, while a trend for a lower systemic exposure was seen in rats on Day 28, and at the highest dose in dogs. The oral bioavailability was estimated to 30-50% after a single dose of 10 mg/kg in rats.

The plasma exposure of C106 following oral administration in both rats and dogs was dependent on dose. The exposure in terms of  $C_{max}$  and area under the plasma concentration *vs*. time curve (AUC) in rats increased more than dose-proportionally following repeated administration of doses up to 40 mg/kg. Overall, a trend for higher exposures was seen in female rats compared to male rats after a single administration, but not after repeated administrations.

In dogs, the plasma exposure increased more than dose-proportionally following repeated administration of doses up to 40 mg/kg, although the supra-proportional increase was less pronounced on Day 28 than on Day 1. Overall, there was no significant sex difference in dogs in the exposure to C106 with no apparent differences seen in absorption or elimination for Day 1 and Day 28.

The plasma protein binding was high in all species, with dogs having the lowest protein binding (on average 97.5% in dog, 99.8% in rat and 99.6% in human), and independent of C106 concentration in the range of 0.1-50  $\mu$ M.

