# Table 8.1-1 Schedule of events, Part A (SAD)

BMI=Body mass index. CTP=Clinical trial protocol. ECG=Electrocardiogram. FSH=Follicle stimulating hormone.

HIV=Human immunodeficiency virus.

1. Details in separate flow chart (Table 8.1-2).

2. For the food-effect cohort, each subject will participate in 2 trial intervention and observation periods separated by a washout period.

3. Or after early withdrawal.

4. Females only (questionable cases).

5. Drug tests may also be performed at 1 to 2 additional random occasions during the trial.

6. Symptom driven physical examination.

- 7. Clinical chemistry, haematology and coagulation, see Section 11.3.5.
- 8. Systolic and diastolic blood pressure, pulse, respiratory rate at all visits indicated. Temperature will be measured on Day -1 only (other visits if indicated). For details regarding vital signs, see Section 11.3.4.
- 9. Ambulatory telemetry starting 30 min (±10 min) pre-dose and ending 24 hours (±20 min) post-dose.
- 10. Cardiodynamic ECG (collect and store) from cohort A2 (*i.e.*, not in cohort A1) and not in the fed part in the food effect cohort.
- 11. High-fat breakfast only for subjects participating in the fed part in the food effect cohort, see Section 10.5.1.
- 12. Day -1 Optional evening snack. Day 1: standardised lunch (at least 4 hours post-dose), optional snack, dinner and optional evening snack Day 2: non-standardised breakfast lunch, optional snack, dinner and optional evening snack. Day 3: non-standardised breakfast. For timing of meals, refer to Table 8.1-2.

# Table 8.1-2 Detailed schedule of events, Part A (SAD) Day -1 to Day 2

Tuble 611 2 Dennieu Seneum	Day -1							Day 1							Day 2 Day				
Assessment/time-point (hh:mm)	Admission	Pre- dose	00:00	00:20	00:40	01:00	01:30	02:00	03:00	04:00	06:00	08:00	10:00	16:00	24 h	48 h			
Inclusion/exclusion criteria		X																	
Urine drug screen	Х																		
Alcohol test	Х																		
Physical examination		Х																	
Clinical Laboratory profile	Х														Х	Х			
Safety urine sampling	X														X	X			
Urinalysis (dipstick)	X																		
Vital signs 	X	X			X			X		X	X		X		X	X			
12-lead safety ECG		X			X			X		X	X		X		X	X			
Telemetry 						1			-X						1				
Randomisation		Х																	
IMP administration			X																
Cardiodynamic ECG 									-X										
PK blood sampling		X		X	X	X	X	X	X	X	X	X	X	X	X	X			

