# 8.3.2 Selection of doses for cohorts 5 and 6 in Part A (SAD)

Based on the interim PK analysis of cohorts 1 to 4 (Table 8.3-2), the planned doses of C106 in cohorts 5 and 6 have been adjusted. The results from the interim PK analysis showed that the plasma exposure of C106 was lower than expected and that C106 exhibited a non-linear PK. The increase in mean  $C_{max}$  and AUCinf for cohort A:4 (180 mg) in comparison to cohort A:3 (60 mg) was 13.2-fold and 7.2-fold, respectively (Table 8.3-2). C106 exhibited a fast absorption with a Tmax of 20-40 minutes and the mean  $C_{max}$  and AUCinf were 2590 ng/mL and 2244 h\*ng/mL, respectively, with a mean T1/2 of approximately 11 hours (Figure 8.3-1). The mean margin to the exposure stopping criteria for Part A cohort 4 was at least 3.4-fold for  $C_{max}$ .

[figure not shown]
For cohorts 5 and 6, the planned doses are 240 mg and 300 mg, corresponding to dose increments of 1.3 and 1.25 times the previous dose, respectively. The dose given in cohort 6 may be adjusted as recommended by the iSRC following evaluation of emerging safety, tolerability, and PK data in cohort 5. Up to 2 additional dose cohorts can be explored based on the safety, tolerability, and PK of the drug, if recommended by the iSRC. The iSRC recommendation, as well as Sponsor's decision, will be documented in a non-substantial amendment to the clinical trial protocol (CTP). For dose escalation and stopping rules in Part A, refer to Table 8.3-3.

			Observed Cmax	Observed AUCinf	Stoppin	g criteria	Margins	Margins	
Cohort	Dose (mg)	N	(ng/mL) Mean (Max)	(h*ng/mL) Mean (Max)	Cmax (ng/mL)	AUC (h*ng/mL)	C max Mean	AUC Mean	
Cohort A:1	5	6	1.65 (2.85)	20.7 (35.0)	8730	15900	5300	770	
Cohort A:2	30	6	82.3 (156)	114 (142)	8730	15900	106	139	
Cohort A:3	60	6	196 (278)	312 (501)	8730	15900	44.5	51.0	
Cohort A:4	180	6	2590 (5130)	2244 (3280)	8730	15900	3.4	7.1	

Table 8.3-2 Observed exposure in humans and margin to stopping criteria

*Figure 8.3-1 Pharmacokinetic mean concentrations for conducted SAD cohorts– logarithmic scale C106 (ng/mL)* 

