# 8.3.3 Maximum exposure and dose

As discussed in detail in Section 6.3, there is considerable evidence in the literature that the infiltration of inflammatory cells in some organs in rats (critical finding for setting the NOAEL in rats) is species specific and of no human relevance. This suggest that the exposures at NOAEL in dogs are more relevant to set a human exposure limit than the NOAEL in rats.

The highest dose of C106 to be tested in this trial (Part A or Part B) shall, thus, not surpass the exposure at NOAEL in the female dog, *i.e.*, a mean value of **8730 ng/mL** and **15900 ng\*h/mL** for Cmax and AUClast, respectively, see Table 8.3-1.

The maximum oral dose in Part A and the maximum oral daily dose in Part B will not exceed 480 mg C106.

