## Table 8.3-3 Dose escalation and stopping rules in Part A (SAD)

 When reviewing emerging data in relation to this criterion, the maximum exposure observed in individual subjects within a cohort rather than the mean exposure should be taken into account. The exposure predictions are normally based on the highest observed Cmax and AUCinf/AUCtau in the previous conducted SAD cohort assuming linear kinetics. If non-linear PK is observed in previously conducted cohorts, this will also be considered.

Stop criterion	Action taken
At individual and dose group level	
If 1 subject on active treatment has an SAE assessed as related to IMP administration	
 
Stop dosing of subject with a potential serious adverse reaction (SAR). Await dosing of additional subjects until the iSRC's recommendation and the Sponsor's decision on continuation.
 
Unblinding of subject with potential SAR. Only voting members of the iSRC will be unblinded.
 
Evaluation by iSRC. The iSRC makes recommendation to Sponsor.
 
Sponsor decides how to proceed: The subject received active treatment, i.e., met stopping criterion: stop further dosing at this dose level for all subjects. Sponsor decides if the
 

If 2 subjects on active treatment in the same cohort have severe, non- serious AEs assessed as related to the IMP administration (independent of within or not	
 
trial will be terminated or if dosing will resume at a lower dose level.
 
1. Stop dosing of subjects with severe, non-serious potential adverse reactions. Await dosing of additional subjects until the iSRC's recommendation and the Sponsor's decision on continuation.
 
2. Unblinding of the subjects with potential adverse reactions. Only voting members of the iSRC will be unblinded.
 

within the same System organ class [SOC])	
 
3. Evaluation by iSRC. The iSRC makes recommendation to Sponsor.
 
4. Sponsor decides how to proceed:
 
Both subjects received active treatment, i.e., met stopping criterion: stop further dosing at this dose level for all subjects. Sponsor decides if the trial will be terminated or if dosing will resume at a lower dose level.
 

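### No PK sample is drawn before 20 minutes although human Tmax is 20–40 minutes, so a Cmax read at the first sample may be too low by an unknown amount

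*Combined protocol and SAP*

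**What the plan says.** Section 8.2 gives the basis for the sampling times: "The time points for PK blood sampling are selected based on data obtained from previous non-clinical studies". Section 6.1.4 describes Cmax in those studies as "reached within 1-4 h in rats and dogs".

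The Part A grid in Table 8.1-2 begins "Pre- dose 00:00 00:20 00:40 01:00 01:30 02:00 03:00". In Part B, Day 1 (Table 8.1-4) and Day 8 (Table 8.1-5) start the same way. No post-dose sample comes before 20 minutes.

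Section 8.3.2, reporting cohorts A1–A4, says that "C106 exhibited a fast absorption with a T max of 20-40 minutes". Its Table 8.3-2 gives, for the top dose so far, "Cohort A:4 180 6 2590 (5130) 2244 (3280) 8730 15900 3.4 7.1": mean (maximum) Cmax and AUCinf, the two limits, and the mean margins.

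The Cmax limit is the female-dog value of 8730 ng/mL. Section 8.3.3 states it as a mean that the highest dose "shall, thus, not surpass the exposure at NOAEL in the female dog". The footnote to Table 8.3-3 is stricter: "the maximum exposure observed in individual subjects within a cohort rather than the mean exposure should be taken into account". The same footnote bases predictions on the highest values "in the previous conducted SAD cohort assuming linear kinetics", and says that observed non-linearity will also be considered.

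Sections 8.1.1 and 8.1.2 let the internal safety review committee (iSRC) adjust PK sampling times on emerging data.

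**The concern.** Observed Tmax falls on the first two post-dose samples and nowhere else. When the maximum is at 40 minutes, there is a sample on each side of it. When it is at 20 minutes there is no earlier sample, so the true peak may already have passed. A concentration read at fixed times cannot exceed the true peak, so any error at that point is downward.

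Cmax is also the tighter of the two exposure limits: the mean margin at 180 mg is 3.4 for Cmax against 7.1 for AUC. An under-read Cmax would make the distance to 8730 ng/mL look larger than it is. The highest individual value carries the prediction for the next dose, and a subject with a very high, sharp peak is the one most likely to have peaked early. Section 8.2 still cites only non-clinical data, although human interim PK is now in the protocol.

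**Working it through.** **1. The plan's own margins (Table 8.3-2, 180 mg).** 8730/2590 = 3.37 and 15900/2244 = 7.09. These reproduce the stated 3.4 and 7.1.

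**2. Margin for the highest individual.** 8730/5130 = 1.70. Linear scaling, the stated default, gives:

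- 240 mg: 5130 × 240/180 = 6840. An under-read of 1 − 6840/8730 = 21.6% would bring it to the limit.
- 300 mg: 5130 × 300/180 = 8550. An under-read of 1 − 8550/8730 = 2.1% would bring it to the limit.
- At 180 mg itself, an under-read of 1 − 5130/8730 = 41% would be needed.

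Once cohort A5 has been read, its data replace the scaling from 180 mg, but on the same sampling grid.

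**3. What AUC/Cmax says about the time of the peak.** In a one-compartment model with first-order absorption, AUC/Cmax = exp(ke·Tmax)/ke. This is smallest at ke = 1/Tmax, so AUC/Cmax ≥ e·Tmax and Tmax ≤ (AUC/Cmax)/e.

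- Mean at 180 mg: 2244/2590 = 0.87 h, so Tmax ≤ 0.87/2.718 = 0.32 h, about 19 minutes.
- Highest-Cmax subject: that subject's AUCinf is at most 3280, so the ratio is at most 3280/5130 = 0.64 h, whether or not both maxima belong to one person. Then Tmax ≤ 0.64/2.718 = 0.235 h, about 14 minutes.

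An absorption lag adds its full length to both bounds. With a 10-minute lag they become about 29 and 24 minutes.

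**4. How much the first sample could miss.** First, one-compartment curves with an assumed early-decline half-life of 0.33–1 h, read at the protocol's times: a true peak at 20–40 minutes is read at 96–100%, at 15 minutes at 96–98%, and at 10 minutes at 82–92%.

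Second, two-compartment curves solved to match the AUC/Cmax ratios above. The terminal half-life is 11 h (from the protocol). The other settings are assumptions: absorption rate 3–12 per hour, terminal phase 5–20% of the area, early decline no faster than absorption, and AUC computed by the linear trapezoid from the protocol's times. Observed Cmax as a share of the true peak:

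| Profile at 180 mg | No lag | 5-minute lag | 10-minute lag |
|---|---|---|---|
| Mean, 0.87 h | 83–100% | about 95–100% | about 90–100% |
| Highest Cmax, 0.64 h | 65–94% | 86–99% | 99–100% |

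For the mean profile with a 10-minute lag, the peak falls after 20 minutes, so the loss lies between the 20- and 40-minute samples and a 10-minute draw would not recover it.

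**5. Dose proportionality.** The least-squares slope of log mean Cmax on log dose over 5, 30, 60 and 180 mg (1.65, 82.3, 196, 2590 ng/mL) is 2.02. A constant proportional under-read shifts every log value equally and leaves the slope unchanged. If only the 180 mg mean is raised by a factor f, the slope moves by ln f × 1.619/6.781. Here 1.619 is the distance of ln 180 from the mean log dose, and 6.781 is the sum of squared distances. For f = 1.1 the change is 0.023 (slope 2.05); for f = 1.2 it is 0.044 (slope 2.07).

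**The case against.** The strongest reply is that no material bias has been shown. The documents give only a Tmax range, not how many subjects peaked at 20 minutes, nor the Tmax of the subject with 5130 ng/mL. If that subject peaked at 40 minutes, the value may need little or no correction. Samples at 20, 40 and 60 minutes bracket a peak inside 20–40 minutes, where step 4 puts the loss at 0–4%. One AUC/Cmax ratio does not identify a curve: a short absorption lag removes most of the loss, and 0.87 h is a ratio of arithmetic means, not a subject's profile. All of this stands. It rules out saying that Cmax is probably biased low.

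A reader might infer that the grid was designed around a 1–4 h peak. Section 8.2 says only that non-clinical data were used, and the grid is dense in the first 90 minutes. The prediction in Section 8.3.1 (CL 5.5 mL/min/kg and V 0.2 L/kg, so ke = 1.65 per hour; Ka 1 per hour) puts Tmax at ln(1.65)/0.65 = 0.77 h, about 46 minutes, which the grid covers.

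Safeguards also exist. The iSRC may change sampling times, the individual maximum is used, and non-linearity is to be considered. Non-linearity is the larger issue for the limit. The 60-to-180 mg exponent is ln(2590/196)/ln 3 = 2.35, and extending it from 5130 gives about 10,080 ng/mL at 240 mg with no under-read at all. That does not answer the sampling point; a steep Cmax curve makes an accurate Cmax more useful.

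Finally, an early draw is not entirely free. Cardiodynamic ECGs are extracted at every PK time to 24 hours in fasted cohorts from A2, after 15 minutes of supine rest. For a 10-minute time point that rest would begin before dosing and span the intake of about 240 mL. The general 10% window would leave only 1 minute either side. The fix has to allow for both.

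**Conclusion.** The point holds as a minor one. A Cmax recorded at 20 minutes is an at-or-before reading, and the grid cannot show whether the peak was missed. The size is unknown. Without an absorption lag it could be a 6–35% under-read for the highest-Cmax subject and 0–17% for the mean profile. With a 10-minute lag it is nearly nothing for the former. These ranges rest on the assumed absorption model and lag, not on data in the protocol.

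The consequence lies with the 8730 ng/mL limit, because linear scaling from 5130 to 300 mg ends only 2.1% below it. A reader might go further, pick a single reading such as 85%, and restate 5130 as 5130/0.85 = 6035 with a margin of 8730/6035 = 1.45. Nothing in the documents fixes that percentage. Nor do they support a claim that the power-model slope is distorted: that would need under-reading to differ by dose, and even a 20% correction at 180 mg alone moves the slope only from 2.02 to 2.07.

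**What to change.** - For the remaining Part A cohorts and for Days 1 and 8 of Part B, add one PK sample at about 10 minutes, with its own time window and no paired cardiodynamic ECG extraction. Add it rather than moving the 1:30 sample, which covers the early decline and keeps AUC comparable with A1–A4.
- Report, per cohort, how many subjects had Cmax at the first post-dose sample. For A1–A4 this needs no new data and would show at once whether the issue is real.
- Update Section 8.2 to cite the human interim PK as a basis for the sampling times.

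Cost: one 5 mL draw per profile from the indwelling catheter. Part A goes from 164 to 169 mL and Part B from 290 to 300 mL (two profiles), against the 450 mL ceiling in Section 12.2. The iSRC can already recommend changes to sampling times. Cross-cohort Cmax tables would need a footnote that A1–A4, and any Part B cohort already dosed, lack the early point.
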